Further details on response confirmation criteria for each histological cohort will be provided in the RAP. Subjects with unknown or missing response will be treated as non-responders; that is, they will be included in the denominator when calculating the percentage.

The observed confirmed ORR will be reported at the final analysis for each histology. The estimates along with 95% exact confidence interval (CI) will be provided.

Bayesian inference based on summary statistics from the posterior distributions of each ORR will be reported. The posterior mean and posterior 2.5% and 97.5% percentiles of the ORR will be calculated for each histology. In addition, the posterior probability that the ORR exceeds its corresponding historical control will be reported for each histology.

Duration of response for the subset of subjects who have a confirmed response (See [Table 31](#)) is defined as the time from first documented evidence of response until the first documented sign of disease progression or death. Duration of response will be summarized descriptively for each histology, if data warrant, using Kaplan-Meier medians and quartiles. Details on rules for censoring will be provided in the RAP.

Progression-free survival (PFS) is defined as the time from the date of enrollment to the earliest date of progression or death. Progression-free survival (PFS) will be summarized by histology, if data warrant, using Kaplan-Meier quartile estimates along with 2-sided 95% CIs. If the subject does not have a documented date of progression or death, PFS will be censored at the date of the last adequate assessment. Further details on rules for censoring will be provided in the RAP. Progression-free survival (PFS) will be reported at the time of final primary analysis for overall response rate (ORR), regardless of the maturity of the data, and then updated at the final analysis.

Overall Survival (OS) is defined as the time from the date of enrollment to the date of death due to any cause. Censoring will be performed using the date of last known contact for those who are alive at the time of analysis. Overall survival (OS) will be summarized by histology, if data warrant, at the time of final primary analysis for overall response rate (ORR), regardless of the maturity of the survival data, and then updated at the final analysis.

Further details including possible sensitivity analyses will be provided in the RAP.

[REDACTED]

[REDACTED]

[REDACTED]

[REDACTED]

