NOTE: For subjects who are transfusion-dependent at baseline, a hemoglobin of ≥ 9 g/dL without transfusions or growth factors for at least 4 weeks.

- circulating hairy cells $\leq 5\%$ of lymphocytes
- $\geq 50\%$ reduction of BM infiltration by hairy cells
- $\geq 50\%$ reduction of palpable disease-related organomegaly.

Subject must have the following (if abnormal prior to treatment):

- $\geq 50\%$ decrease or normalization ($< 5000/mm^3$) in peripheral blood lymphocyte count from the pre-treatment baseline value
- $\geq 50\%$ reduction in lymphadenopathy, based on sum of products of perpendicular diameters, or resolution to size consistent with CR
- $\geq 50\%$ reduction in abnormal hepatosplenomegaly by imaging, or resolution to size consistent with CR

Minor response (MR): requires all of the following:

- $\geq 50\%$ reduction of circulating hairy cells

- Improvement of one or more of the peripheral blood counts (ANC, platelets or hemoglobin).

Relapse: defined as the reappearance of leukemia/lymphoma in a subject who previously achieved a CR or documentation of PD in a subject who previously achieved a PR

Stable Disease (SD): defined as not meeting the criteria for CR, PR, MR or PD

Disease progression (PD): defined as the occurrence of at least one of the following compared to pre-treatment:

- $\geq 50\%$ increase in the sum of the products of the greatest perpendicular dimensions of at least two lymph nodes on two consecutive examinations at least 2 weeks apart (at least one node must be ≥ 2 cm in minimum length) or appearance of new palpable lymph nodes
- $\geq 50\%$ increase in the absolute number of circulating lymphocytes, on two consecutive examinations showing abnormal lymphocytosis at least 2 weeks apart
- $\geq 25\%$ decrease in hemoglobin (must be $< 10\text{g/dL}$), platelets (must be $< 100,000/\text{uL}$), or ANC (must be $< 1500/\text{uL}$) unless these are judged to be effects of treatment.

References:

Kreitman RJ, Fitzgerald DJ, Pastan I. Approach to the patient after relapse of hairy cell leukemia. *Leuk Lymphoma*. 2009a;50(suppl 1):32-37.

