2.6.1 Duration of response

For the subset of subjects who show a confirmed response as defined for each cohort in [Error! Reference source not found. 2.4.1](#), duration of response (DoR) is defined as the time (in weeks) from the first documented evidence of response (the first response prior to confirmation) until the time of documented disease progression or death due to any cause.

For the cohorts assessed using RECIST 1.1 and RANO criteria, the analysis of DoR will be based on radiological response from investigator assessment. The date of disease progression is defined as the date of radiological disease progression based on the appropriate disease response criteria. Clinical progression, defined as investigator assessed clinical progression in the absence of radiological confirmation, is not considered a progression event in this analysis. Specifically, in the event of clinical progression leading to discontinuation of study treatment and radiological assessment, if radiological assessments do not indicate radiological progression, then the subject will be censored at the time of last radiological assessment. If a subject has not progressed, not died, and not started new anti-cancer therapy, DoR will be censored at the date of the last adequate assessment.

For the HCL cohort, the overall investigator-assessed response will be used to determine timing of response and/or progression. Relapsed disease will be considered as progression for the analysis.

Details of censoring after extended time without adequate assessment are given in section 4.2.

For subjects who receive subsequent anti-cancer therapy, the following rule will apply:

- If anti-cancer therapy is started without documented progression or is started prior to progression, then DoR will be censored at the date of the last adequate disease assessment that is no later than the date of initiation of anti-cancer therapy (i.e. if disease assessment occurs on the same day as the start of new anti-cancer therapy then the assessment will be used, as it will be assumed that the assessment occurs prior to the administration of new anti-cancer therapy).

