2.6.2 Progression-free survival

Progression-free survival (PFS) is defined as the interval (in weeks) between the first dose of study treatment and earlier date of disease progression or death due to any cause.

For the cohorts assessed using RECIST 1.1 and RANO criteria, the primary analysis of PFS will be based on radiological response from investigator assessment. The date of disease progression is defined as the date of radiological progression based on imaging data. Subjects who do not meet the RECIST 1.1 or RANO criteria for progression and are still alive will be censored. Clinical progression, defined as investigator assessed clinical progression in the absence of radiological confirmation, is not considered a progression event in this analysis. Specifically, in the event of clinical progression leading to discontinuation of study treatment and radiological assessment, if radiological assessments do not indicate radiological progression, then the subject will be censored at the time of last radiological assessment. If a subject has not progressed, not died, and not started new anti-cancer therapy, PFS will be censored at the date of the last adequate assessment. For the HCL cohort, the overall investigator-assessed response will be used to determine timing of progression.

Details of censoring after extended time without adequate assessment are given in section 4.2.

For subjects who receive subsequent anti-cancer therapy, the following rule will apply:

- If anti-cancer therapy is started without documented progression or is started prior to progression, then PFS will be censored at the date of the last adequate disease assessment that is no later than the date of initiation of anti-cancer therapy (i.e. if disease assessment occurs on the same day as the start of new anti-cancer therapy then the assessment will be used, as it will be assumed that the assessment occurs prior to the administration of new anti-cancer therapy).
- If a subject does not have an adequate post-baseline assessment that is no later than the date of initiation of anti-cancer therapy, PFS will be censored at the date of the first dose. If any adequate post-baseline assessment exists after the date of initiation of anti-cancer therapy, the reason for censoring will be recorded as “new anti-cancer treatment started prior to disease progression”. Otherwise if no adequate post-baseline assessments exist,

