4.2 Extended Loss to Follow-up or Extended Time without an Adequate Assessment

Since missing scheduled disease assessments prior to progression or death increases the uncertainty about when the event actually occurs, PFS and DoR will be censored for subjects who have progression or die after missing two or more scheduled disease assessments. Specifically, if there are two or more scheduled assessments which are missing followed by progression or death, PFS and DoR will be censored at the last adequate assessment prior to progression or death.

For the purpose of this calculation, the last adequate assessment is defined as the last assessment prior to progression or death with response other than NE or missing.

For solid tumor cohorts (ATC, BTC, GIST, NSGCT/NGGCT, ASI, WHO Grade 1 or 2 Glioma and Grade 3 or 4 Glioma) and MM cohort, when the scheduled disease assessment is every 8 weeks (for the first 48 weeks of study treatment), a window of 119 days (16 weeks + 7 day window) will be used to determine whether there was an extended time without adequate assessment. When the scheduled disease assessment is every 12 weeks (after the first 48 weeks of study treatment), a window of 175 days (24 weeks + 7 day window) will be used to determine whether there was an extended time without adequate assessment. Specifically, extended lost-to-follow-up period is defined using different time windows as described in [Table 4-1](#).

Table 4-1 Extended lost-to-follow-up period at different study times

Last adequate assessment	Extended lost-to-follow-up period
<= end of week 44	16 + 1 weeks (119 days)

Last adequate assessment	Extended lost-to-follow-up period
(<=308 days)	
>= beginning of week 45 – <= end of week 54 (>308 days, <=378 days)	20 + 1 weeks (147 days)
>= beginning of week 55 (>378 days)	24 + 1 weeks (175 days)

For the HCL cohort, the scheduled disease assessment is every 4 weeks for the first 48 weeks of study treatment, then at least every 8 weeks for patients tolerating the study drug in the judgement of the treating investigator. Following protocol amendment 11, the interval between assessments beyond the first 48 weeks is increased to at least every 12 weeks. To provide reasonable allowance for missed assessments within the new schedule, the same rules will be used for HCL as for the solid tumor cohorts and MM to determine whether there was an extended time without adequate assessment.

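### The SAP counts relapse of hairy cell leukemia as progression for duration of response but gives no such rule for PFS, so the two endpoints can disagree for the same visit

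*SAP*

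**What the plan says.** SAP 2.6.1 (duration of response) has two HCL sentences. The first says that "the overall investigator-assessed response will be used to determine timing of response and/or progression". The second says "Relapsed disease will be considered as progression for the analysis".

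SAP 2.6.2 (PFS) has one HCL sentence: "For the HCL cohort, the overall investigator-assessed response will be used to determine timing of progression". No relapse rule follows it. PFS ends at the "earlier date of disease progression or death due to any cause". Protocol 18.3.3.2 describes PFS as "the time from the date of enrollment to the earliest date of progression or death" and has no relapse rule either.

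Protocol Appendix 12 keeps two separate entries for HCL:

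- Relapse after complete response is "defined as the reappearance of leukemia/lymphoma in a subject who previously achieved a CR". For a partial responder, relapse requires documented progressive disease.
- Progressive disease is "defined as the occurrence of at least one of the following compared to pre-treatment". The list covers nodal growth or new palpable nodes, a rise in circulating lymphocytes, and a fall in hemoglobin, platelets or neutrophils.

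Under SAP 2.6.2, a subject who starts new anti-cancer therapy without documented progression is censored at the last adequate assessment on or before that start. SAP 4.2 gives the meaning of adequate for its missed-assessment rule: "the last adequate assessment is defined as the last assessment prior to progression or death with response other than NE or missing".

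**The concern.** For any confirmed responder, PFS and duration of response should end on the same date and differ only in where they start. In the RECIST and RANO cohorts this holds, because both endpoints use the same radiological progression. In HCL the SAP added a relapse rule to one endpoint and not to the other.

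Relapse is an important form of failure after complete response in this disease. If it ends duration of response but not PFS, the PFS curve loses real failures and the two endpoints contradict each other in one report. PFS and duration of response are both secondary objectives, and Amendment 11 extended the study to obtain more mature estimates of them. HCL then supplied 36 of the 55 subjects still on treatment. SAP 2.6.2 notes that HCL has no independent review, so no second PFS analysis would reveal the difference.

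**Working it through.** The documents state no HCL figure for PFS or duration of response, so there is nothing to reproduce. The check is a comparison of texts, with arithmetic only on the Appendix 12 thresholds.

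**Step 1. Can relapse after complete response occur without progressive disease?** Appendix 12 sets the hemoglobin floor for complete response at 11 g/dL. Progression on hemoglobin needs a fall of at least 25% from pre-treatment, to below 10 g/dL. One of the alternative HCL entry criteria (protocol 5.4.1.1.8) is hemoglobin below 10 g/dL.

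- Pre-treatment value at that limit: 0.75 × 10 = 7.5 g/dL. From the floor of 11, this is a fall of (11 − 7.5)/11 = 31.8%.
- Assumed pre-treatment value of 8 g/dL: 0.75 × 8 = 6.0 g/dL. From the floor of 11, this is a fall of (11 − 6)/11 = 45.5%.

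A complete responder whose hairy cells reappear while hemoglobin lies between the progression threshold and 11 g/dL has relapsed. That subject has not progressed on hemoglobin. Platelets and neutrophils follow the same 25% rule against pre-treatment. Circulating lymphocytes need a 50% rise over pre-treatment. New palpable nodes are the exception, because they count as progression with no percentage threshold. So relapse without progression is possible, although not every relapse will be of that kind.

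**Step 2. What does each endpoint do with that visit?**

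| | Duration of response (SAP 2.6.1) | PFS (SAP 2.6.2) |
|---|---|---|
| Source of HCL timing | Investigator's overall response | Investigator's overall response |
| Relapse rule | Counts as progression | None stated |
| Relapse without progressive disease | Event | No event on a literal reading |
| New therapy starts afterwards | Event already recorded | Censored at last adequate assessment |

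**Step 3. A dated example (assumed dates).** Complete response is first documented at week 16, relapse without progressive disease at week 100, and new therapy at week 104. Duration of response is an event at 100 − 16 = 84 weeks. If the relapse visit carries a response that is neither not-evaluable nor missing, it fits the SAP 4.2 description of an adequate assessment. PFS is then censored at week 100. The same visit closes one endpoint as a failure and the other as a censoring, and the censoring table would attribute it to new therapy before documented progression. If no new therapy starts, PFS stays open until progression, death or the last adequate assessment.

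**Step 4. Direction.** In the first case an event is replaced by a censoring that is itself caused by treatment failure, which is informative. In the second the PFS time is lengthened. Both raise the Kaplan-Meier curve.

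**Step 5. Who is affected?** Only complete responders. For partial responders Appendix 12 makes relapse depend on documented progressive disease, so both endpoints use the same event.

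**The case against.** The strongest reply is that the SAP is silent rather than contradictory. A reader might infer that relapse is excluded from PFS. The text does not say so. Both sections draw HCL timing from the investigator's overall response, and an investigator may record relapse as progressive disease. The eCRF options and the table shells, which could settle this, are not among the documents. This stands, and it limits the claim to a literal reading. It does not remove the gap: if relapse were always recorded as progression, the relapse sentence in 2.6.1 would not be needed.

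Second, SAP 2.6.1 already gives a separate HCL analysis of complete response duration, which ends at the first adequate assessment that is not a complete response, or at death. Loss of complete response is therefore reported. That analysis covers complete responders only and leaves PFS as it is.

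Third, few subjects may be affected. In April 2020, about 21 months after enrollment ended, 36 HCL subjects were on treatment and 7 in follow-up, and Amendment 11 refers to durable HCL responses. This is fair, and it is a reason not to attach a number to the bias.

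Fourth, a reader might go further and object to the pre-treatment reference itself, because a partial responder could lose the response and return to entry counts without progressing. Appendix 12 states that its criteria are adapted from a guideline, a consensus resolution and earlier HCL studies. The reference point is disclosed and is the same for both endpoints, so it is not an inconsistency. Counting a 25% fall from the best on-treatment value as an event would also misclassify responders. Neutrophils of 0.5 rising to 1.2 and falling to 0.9 (×10⁹/L) are down 25% from best, since 0.9/1.2 = 0.75. They are still 80% above baseline, since 0.9/0.5 = 1.8, and so still meet the neutrophil criterion for partial response.

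**Conclusion.** The point holds as an inconsistency between two SAP sections. Followed literally, the plan makes relapse after complete response an event for HCL duration of response and not for HCL PFS, whenever no progression criterion is met. HCL PFS would then be biased upward.

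This rests on two conditions: that some complete responders relapse without meeting a progression criterion, and that investigators do not record those relapses as progressive disease. Where they do, there is no effect.

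A reader might infer a bias of several percentage points. The documents do not support any figure, because they give no HCL complete response rate, no relapse rate and no total HCL enrollment. It would also be too strong to say that PFS always runs past relapse, because in a subject who starts new therapy at relapse the effect is a lost event.

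The change should be made but is not critical. HCL PFS is a secondary, descriptive Kaplan-Meier summary, and the declaration of activity in a cohort depends on response rate alone.

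**What to change.** In SAP 2.6.2, after the HCL sentence, add for HCL the rule already in 2.6.1: "Relapsed disease will be considered as progression for the analysis". State that the event date is the date of the visit at which relapse was recorded, which agrees with SAP 4.3, where HCL response dates are visit dates.

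The cost is one sentence and a matching line in the PFS derivation. No new data are needed, because the relapse records and dates already feed duration of response. HCL PFS may become slightly less favourable.

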2.6.3 Overall survival

Overall survival (OS) is defined as the time (in weeks) from first dose until death due to any cause. The length of this interval is estimated as the date of death minus date of first dose plus 1 day. Subjects who have not died will be censored at the date of last contact (as recorded in the eCRF). The last date of contact will be defined as the maximum date of any visit date, survival follow-up date, or date of study withdrawal. Only patient contacts recorded in the eCRF can be used for the calculation of last date of contact.

Overall survival will be summarized descriptively and graphically using Kaplan-Meier method. The Kaplan-Meier estimate for the median overall survival time and the first and third quartiles will be presented, along with approximate 95% confidence intervals. Brookmeyer-Crowley method will be used for the confidence interval calculation. Overall survival at 6 months, 12 months and 24 months will be summarized using the Kaplan-Meier method.

Listing of overall survival data will also be provided.

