45. **PK Sampling - Week 8, Week 12, and Follow-up Visit:** A single 2 mL blood sample for PK analysis of trametinib, dabrafenib and its metabolites (hydroxy-dabrafenib and desmethyl-dabrafenib) will be collected at Week 8 (pre-dose), Week 12 (pre-dose), and at the Follow-up Visit. Subjects with morning clinic visits are to be instructed to withhold their morning doses of study treatment and PK samples will be collected prior to dabrafenib administration. Subjects with afternoon clinic visits are to be instructed to take their morning doses as usual and PK samples will be collected 4 to 8 hrs following dabrafenib administration. **Samples at the Follow-up Visit are no longer requested for collection as of Protocol Amendment 11.**

[REDACTED]

- 
54. **STUDY TREATMENT:** Subjects must receive their supply of study treatments within 3 days of enrollment.
55. **FOLLOW-UP VISIT:** The Follow-up Visit should take place within 28 days (+7 days) of the last dose of study treatments. If the subject is unable to return to clinic, site staff is encouraged to call subject for assessment of AEs.
56. **FOLLOW-UP VISIT:** All safety and laboratory assessments should be performed unless the assessments were performed within 4 weeks prior to the Follow-up Visit.
57. **FOLLOW-UP VISIT:** If the last cardiac assessment was >12 weeks prior to the Follow-up Visit, an ECHO should be performed.
58. **EXTENDED FOLLOW-UP:** The following evaluations will be performed for all patients in all cohorts.
- a) Dermatologic exam. Exams will be performed every 4 weeks (+/-7 days) for the first 6 months. The skin will be carefully examined and pictures and biopsy will be taken of any new or changed skin lesions.
 - b) If study treatments are permanently discontinued prior to the subject having confirmed disease progression, the subject will continue to have disease assessments every 12 weeks (+/-14 days) until disease progression or initiation of new anti-cancer treatment, or death, whichever comes first.
 - c) Subjects will be followed every 12 weeks (+/-14 days) for survival until the subject dies or withdraws consent or is lost to follow up, or up to a time period as defined in Section 16.3. Survival follow up may be performed via clinic visit, a telephone contact, an email or by mail. The initiation of any new anti-cancer treatment(s) and date of last contact should also be documented.

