16.6 Subject Withdrawal Procedures

If subject is withdrawn from study treatment due to an AE or SAE, subject should be followed until:

- AE or SAE stabilizes or resolves
- AE or SAE is otherwise explained
- Subject is lost to follow-up

If subject is withdrawn from study treatment with an ongoing Grade 3 or 4 laboratory abnormality:

- Subject should be followed until laboratory abnormality improves to Grade 2 or less, unless condition is unlikely to improve due to underlying disease, or resolves

Should a subject fail to attend the clinic for a required study visit, the site should attempt to contact the subject and re-schedule the missed visit as soon as possible. The site should also counsel the subject on the importance of maintaining the assigned visit schedule and ascertain whether or not the subject wishes to and/or should continue in the study based on previous non-compliance. In cases where the subject does not return for the rescheduled visit or cannot be reached to reschedule the missed visit, the site should make every effort to regain contact with the subject (three telephone calls and if necessary a certified letter to the subject's last known mailing address) so that they can appropriately be withdrawn from the study. These contact attempts should be documented in the subject's medical record. Should the subject continue to be unreachable, then and only then will he/she be considered to have withdrawn from the study with a primary reason of "Lost to Follow-up". For all other subjects withdrawing from the study, an alternative reason for discontinuation should be recorded in the eCRF.

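### The OS last-contact date in SAP 2.6.3 includes the study-withdrawal date with no exception for subjects lost to follow-up; applied literally, it would censor them late and bias OS upward

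*SAP*

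**What the plan says.** - **SAP 2.6.3** censors subjects who have not died at the date of last contact recorded in the eCRF, and builds that date as "the maximum date of any visit date, survival follow-up date, or date of study withdrawal". The next sentence adds: "Only patient contacts recorded in the eCRF can be used for the calculation of last date of contact".
- **Protocol 18.3.3.2** states the rule as: "Censoring will be performed using the date of last known contact for those who are alive at the time of analysis". SAP section 3 reports no changes to the protocol-specified analyses.
- **Protocol 16.6** sets out what happens when a subject cannot be reached. The site makes "three telephone calls and if necessary a certified letter to the subject's last known mailing address". It continues: "Should the subject continue to be unreachable, then and only then will he/she be considered to have withdrawn from the study", with loss to follow-up as the primary reason.
- **Protocol 7.1, footnote 58(c)** gives the survival schedule: "Subjects will be followed every 12 weeks (+/-14 days) for survival until the subject dies or withdraws consent or is lost to follow up". The same footnote asks for the date of last contact to be documented.
- OS is a secondary endpoint (SAP 2.6), summarised descriptively by Kaplan-Meier with estimates at 6, 12 and 24 months (SAP 2.6.3).

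**The concern.** A subject who withdraws consent in person is normally known to be alive on the withdrawal date, so using that date is sound. A subject who is lost is different. By Protocol 16.6 the withdrawal follows a missed contact and a series of failed attempts, and vital status on that day is unknown. SAP 2.6.3 does not separate the two cases, and a maximum of three dates picks the latest.

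If the latest date is administrative, the subject sits in the Kaplan-Meier risk set from last contact to withdrawal with no possibility of a recorded death. That adds event-free time to the denominator. It can only lower the apparent hazard and raise the curve, in every cohort that has such a subject. Obtaining more mature OS estimates was one stated reason for the one-year extension in Amendment 11, so the late part of the curve matters here.

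**Working it through.** **1. The passages side by side, for a lost subject**

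| Text | Date it gives |
|---|---|
| Protocol 18.3.3.2 | last known contact |
| SAP 2.6.3, list of three dates | the withdrawal date, if later than the last visit or survival contact |
| SAP 2.6.3, next sentence | last patient contact, if read as excluding administrative dates; no change, if read as limiting the data source to the eCRF |

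The two SAP sentences agree for withdrawal in person. For a lost subject they agree only if the eCRF withdrawal date is itself the last contact.

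**2. Inputs for the size**

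The documents give no number lost, no lag and no OS assumption, so there is no plan figure to reproduce. Assumed:
- exponential OS, true median 12 or 24 months;
- loss independent of death, 6% to 18% of subjects lost over follow-up;
- administrative censoring uniform over 36 to 72 months;
- lag D = 3 months. One contact interval is 12 weeks, or 84/30.4375 = 2.8 months; with the 14-day window it is 98/30.4375 = 3.2 months.

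**3. Formula**

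Let λ = ln 2/median, γ the monthly loss rate and k = λ + γ. Suppose lost subjects stay at risk for D months with no recorded deaths. At time u > D, the ratio of lost-but-still-counted subjects to those truly followed is q = (γ/k)(e^(kD) − 1). The apparent hazard is λ/(1 + q). For u < D the average ratio is q0 = (γ/k)[(e^(kD) − 1)/(kD) − 1]. The apparent 24-month survival is then approximately

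S(24) = exp{−[λD/(1 + q0) + λ(24 − D)/(1 + q)]}.

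The share lost is (γ/k){1 − (e^(−36k) − e^(−72k))/(36k)}, which fixes γ.

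**4. Upper end: median 12 months, 18% lost, D = 3**
- λ = 0.05776; γ = 0.0131; k = 0.07086. Check of share lost: 0.1849 × (1 − 0.0282) = 0.180.
- q = 0.1849 × 0.2369 = 0.0438; q0 = 0.0211.
- Cumulative hazard = 0.1697 + 1.1621 = 1.3318, against a true value of 1.3863.
- S(24) = 26.4% against 25.0%: **+1.4 points**.

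**5. Lower end: median 24 months, 6% lost, D = 3**
- λ = 0.02888; γ = 0.00233; k = 0.03121. Check of share lost: 0.0747 × (1 − 0.1953) = 0.060.
- q = 0.0747 × 0.0982 = 0.0073; q0 = 0.0036.
- Cumulative hazard = 0.0863 + 0.6021 = 0.6884, against a true value of 0.6931.
- S(24) = 50.2% against 50.0%: **+0.2 points**.

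A simulated Kaplan-Meier with 400,000 subjects per setting gives the same range.

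**6. Shorter lag and no lag**

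Clinic visits on treatment are every 4 weeks, so a subject lost on treatment could have a shorter lag. With 10% lost within 36 months and a 4-week lag, S(24) is 25.2% against 25.0% (median 12) and 50.2% against 50.0% (median 24). With D = 0, q = 0 and the bias vanishes.

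**The case against.** The strongest reply is the sentence directly after the list. Read with the term last contact, it excludes an administrative date, and SAP and protocol then say the same thing. That reading is reasonable and, if applied, removes the problem. But the sentence can equally be a limit on data source, ruling out contacts held outside the eCRF, and the preceding sentence names the withdrawal date without condition. A programmer could defend either result.

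A second reply is that Protocol 16.6 says when a subject is considered lost, not which date the eCRF field holds. If sites enter the last contact there, nothing goes wrong. This stands: the eCRF is not among the documents, and the concern is conditional on that field.

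Third, the withdrawal date has a proper use for withdrawal of consent and for subjects transitioned off the study at closure, where it is normally a real contact. This also stands, so the rule needs an exception and need not be replaced throughout.

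A reader might infer that the maximum guarantees the late date, that every OS estimate is inflated, or that the SAP flatly contradicts the protocol. The documents do not support any of these: the limiting sentence may apply, a cohort with nobody lost is unaffected, and the conflict arises under only one reading. Nor do they support large effects. Lags of 6 or 12 months would give +0.5 to +2.8 or +0.8 to +5.6 points under the same assumptions, but the contact schedule supports only about 3 to 4 months.

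**Conclusion.** The text of SAP 2.6.3 is defective for subjects lost to follow-up: two adjacent sentences do not settle which date to use, and one reading departs from the protocol. Under that reading the bias is upward. Confidence in the textual defect is high.

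Confidence in its size is low. The figure of about 0.2 to 1.4 points on 24-month OS rests wholly on the assumed medians, loss share, independent loss and 3-month lag. An upward bias in the reported OS is not demonstrated; it follows only if the maximum is applied as written, subjects are lost, and the recorded withdrawal date is later than their last contact.

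OS is a descriptive secondary endpoint with no test or comparator, so the point is minor to moderate.

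**What to change.** Define last contact as the last date on which the subject was known to be alive: a visit, an assessment, a dose, or a survival follow-up with status alive. Allow the withdrawal date only where it records an actual contact with the subject known to be alive, such as withdrawal of consent. Never use it where the reason is loss to follow-up.

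The data needed are already planned: Protocol 16.6 has the reason for withdrawal recorded in the eCRF, and footnote 58(c) has the date of last contact documented. A listing of living subjects whose withdrawal date is later than their last visit or survival contact would show whether any estimate changes.

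The cost is one SAP sentence and a small change to the derivation. OS may look slightly less favourable.
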